## 8.0 Study Endpoints

### 8.1 Covariates.

Patient characteristics: Socio-demographic characteristics, language, country of origin, time in US, comorbidities, social support, cognition (the cognitive assessment will not be completed if the baseline interview is completed over the phone), and health status will be collected. A literacy assessment using the Newest Vital Sign (NVS) and brief health literacy screener, and the Consumer Health Activation Index (CHAI) will be administered.

Regimen characteristics: Rx drugs will be collected and grouped into drug class. Regimen complexity will be calculated via the Medication Regimen Complexity Index (MRCI).

Provider-Patient Prescription Communication: We will ask questions adapted from the Consumer Assessment of Health Providers Survey (CAHPS-modified only as

necessary) to evaluate the extent and quality of provider verbal counseling on prescription medications.

**Fidelity (Process) Measures:**

- *Receipt of UMS materials.* We will collect EHR data on prescriptions and end-of-visit summaries to assess whether the UMS sigs were actually prescribed and whether the MedSheets and Medlists were printed. Similarly, we will review patients' actual medication bottles to determine if the labels reflect the UMS instructions and ask whether they received the MedSheets and Medlists (yes/no).
- *Receipt of SMS text reminders.* At each follow-up, the RC will ask whether patients received text reminders. We also will have texting opt out data from the text message provider.
- *Use of Patient Portal.* At each follow-up, the RC will inquire whether patients used the Patient Portal and if clinic staff followed-up with the patient. We also will obtain data through the EHR on who has accessed the portal and the number of portal logins each participant did during the study.

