## 8.2 Primary Endpoints.

**Effectiveness Outcomes.** For the outcomes described below, we only include Rx chronic medications. Though we document them, we exclude PRN, as adherence concerns are different.

**Treatment knowledge.** Patients will be asked to identify drug indication; binary classifications will be applied per drug.

**Medication adherence.** The ASK-12 Adherence Barrier Survey assesses patients' general adherence behaviors and barriers to treatment adherence. Adherence will also be measured for each Rx medication using: 1) Self-report of how many pills and how often each medicine was taken over the last 24 hours. The RC will record how many pills were taken at each time for each medicine. Correct dosing will be measured as yes/no per drug, based on having properly demonstrated dose (# pills), spacing (hours between doses), frequency (times per day), and total pills/day, 2) in-person/phone pill counts of all chronic, pill form medicines, using established guidelines employed by our team [R01HS00167; PI [name]], 3) the proportion of days covered (PDC), a measurement of days covered with medication, based on pharmacy claims. This is calculated by summing the number of days' supply obtained by a patient during a given time period and dividing by the number of days for which the medication was prescribed. For each patient, we will assess adherence within drug class. If a patient fills a prescription for a drug and switches to another drug within the same class, all prescriptions will be summed in the numerator. Adherence will be treated both continuously (PDC) and dichotomously (yes/no - PDC  $\geq 80\%$ ). Patients will be asked to sign a release at their first and/or last interview allowing us to obtain fill information from pharmacies used during the study. We will request information from pharmacies 6 months prior to baseline to a year post baseline. If the interview is completed over the phone, patients may receive a pharmacy release form by mail to sign and return to the research team. For the pill count during phone interviews, RCs will read a standardized script to ask patients to count study pills using a standardized procedure. If able, participants will be asked to join a video call so the

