RC can take a screen shot of the patient's remaining pills-per bottle. The RC will save the screen shot/photograph to the study project folder within the secure GIM server only using the patient's studyid to identify the photograph. No PHI will be captured in the photograph. If the participant does not have video capabilities, the RC will proceed to explain how the patient can count their pills and relay the number to the RC. This script is outlined in the interview script. For patients consented before May 19, 2020 that complete a phone 6 month, a brief script will be read informing patients of the change in the consent in regards to the pill count. The RC will ask the participant to provide verbal consent to allow the study team to take a screen shot/photograph of the patient's pills during a video call in order for the RC to count the pills after the interview. The patient will be notified that no PHI will be captured in the photograph.

**Medication reconciliation.** Chart reviews will determine whether any discrepancies are present between patient self-report and the chart medication list. Nature of the discrepancy (omission vs. commission) will be recorded.

**Clinical Outcomes.** Systolic/diastolic blood pressure will be collected on all patients during the baseline and 6 month interview. Low-density lipoprotein cholesterol (LDL) will be obtained from patients' electronic health records. Chart review of hemoglobin A1c (hbA1c) will be reviewed for all diabetic patients. Differences will be measured between the last clinical measurement prior to baseline assessment and the last measured value during the study period (closest to 6 month assessment).

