The UMS EHR tools have been piloted in Epic and Cerner, and are now being implemented in GE Centricity for this proposal now. Among 144 patients at the NMFF General Medicine clinic, nearly all (91%) patients received their MedList, UMS sigs, and MedSheets for new medications; 85% reviewed it with their doctor. Feedback from 20 physicians offered unanimous positive feedback on the tools. [R18HS17220].

**9.14 SMS Text Reminders.** For those patients receiving text reminders (SMS; SMS+Portal), daily text reminders will be sent post baseline following the UMS intervals. The texts will continue daily, with the option to opt out at any time. Stopping the texts will not impact their continuance in the study. Texts will automatically stop after 6 weeks, with an option at that time for patients to opt back in to the service. Those who opt back in will get the texts all 6 months of the study, or until they decide to stop. In past studies we have sent texts for one week, but recent studies have shown patients may benefit from longer text interventions. A covariate will be to look at the effect of length of text intervention to patient adherence, as well

as whether or not people opted out. Participants without unlimited texting plans will be reimbursed the total cost of receiving the texts. Patients will receive uniform, generic messages around UMS time intervals such as, “Good Morning! Please remember to take your medicines today.” and, “Hope you had a great day and remembered to take all your medicine!”

We will use EZ Texting, a safe, economical, premium Internet SMS text service plan, to program and schedule discrete UMS-centered text messages. These will be sent at standard intervals for all patients based on their regimen, with a maximum of two times a day (i.e. 1 or 2 times daily depending on regimen). Because these reminders are sent daily, we have limited the number of times sent per day so as not to burden and overwhelm the patient. Generic reminders are used due to the complexity of patient regimens and the SMS text message itself sent around the general time of behavior is a memory support. The premium plan ensures patients do not receive promotional messages with the text. A trained RC will orient and confirm patients can retrieve text messages. The RC will also instruct patients to abstain from reading text messages while driving and instead read messages and take medicines once they can safely concentrate on the task.

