**9.15 EHR Web-Based Patient Portal.** The addition of the patient portal will provide opportunities to have ongoing communications with their clinic, real-time reconciliation and updating of medication lists, access to regimen-specific medication information, and to provide a feedback loop informing healthcare providers of adherence-related behaviors and concerns. The encrypted patient portal website will be managed by the Alliance HIT team and the MyChart team, under [name] supervision. Secured instant messaging and email features to communicate with clinic staff are already available within the portal. The additional build out above these informational and communication features will be a periodic requests for patients to (1) identify if they missed taking any of the medicine in their regimen in the past 3 days, and (2) list any concerns or problems related to refill, cost, side effects, or management of their medicines. This process has previously been piloted with patients and can be performed in three minutes or less. Patients in this arm will be asked to fill this survey out 2 weeks, 1, 2, 3, 4, and 5 months post baseline. An email will be sent to patients at these time points, requesting that they access the portal and complete the regimen adherence assessment (embedded in the portal). The information submitted back by the patient will be sent back to the EHR and directed to the responsible doctor or nurse. Identified ‘champions’ at Erie and NMHC will be trained to review the files and identify patients with regimen-related concerns. Patients who do not complete the assessment within 48 hours will be sent a second email reminder. If they still do not fill out the survey, a third and final reminder will be sent. Patients who self-report any concerns or who demonstrate incorrect or missed doses will also trigger nurse follow-up. The RC will create a MyChart or MyErieHealth account for patients that do not already have a patient portal account, depending on the clinic they attend. For Erie patients, a MyErieHealth account will be created through the MyErieHealth admin page. For Northwestern patients, the RC will obtain a MyChart activation code by accessing a patient's chart through Epic. Erie staff will send encrypted emails weekly or as needed to NU RC's with a list of patients that have completed the portal survey. For Northwestern patients, RC's will

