determine if a survey was completed by accessing a patient's chart through Epic to see a record of a completed UMS Portal MyChart survey.

**9.16 Nurse Training.** Nurses will be educated on health literacy and health communication best practices, barriers to medication self-management, and how to briefly counsel patients via face-to-face and telephone using teach-to-goal and implementation intention approaches. Our team has used these techniques in prior studies that tested a low literacy diabetes education strategy in FQHCs. Patients at the time of enrollment will also be extensively oriented to the patient portal and use of the EHR and portal tools. The clinic nurse phone number and email will be provided for technical support.

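### The research coordinator role that holds arm and portal-engagement information also records the 24-hour recall and counts pills, and the plan states no assessor masking or separation of tasks

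*Combined protocol and SAP*

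**What the plan says.** **Tasks that reveal arm or engagement.**

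- SMS set-up (9.14): "A trained RC will orient and confirm patients can retrieve text messages".
- Portal set-up (9.15): "The RC will create a MyChart or MyErieHealth account for patients that do not already have a patient portal account".
- Portal-survey completion at Erie (9.15): "Erie staff will send encrypted emails weekly or as needed to NU RC's with a list of patients that have completed the portal survey".
- Portal-survey completion at Northwestern (9.15), where the RCs work from the chart: "determine if a survey was completed by accessing a patient's chart through Epic".
- Follow-up questions (8.1, Fidelity (Process) Measures): "At each follow-up, the RC will ask whether patients received text reminders", and "At each follow-up, the RC will inquire whether patients used the Patient Portal and if clinic staff followed-up with the patient".

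**Tasks that produce the outcome.**

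- 24-hour recall (8.2): "The RC will record how many pills were taken at each time for each medicine".
- Pill count by phone (8.2, 9.11): some 6-month interviews are done by phone. Patients who consented before May 19, 2020 and have one are read an added script, and the permission sought is worded as follows: "allow the study team to take a screen shot/photograph of the patient's pills during a video call in order for the RC to count the" (the object being the remaining tablets, counted once the call is over). Without video, the patient counts and relays the number.

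**Who does this, and why it bears on the primary result.** Section 9.2 gives the RCs and the project manager consent, interviews, retention, follow-up and quality assurance as one block of duties. Section 20.1 lists two bilingual RCs. Section 11.2 sizes the trial on adherence by 24-hour recall at six months. Section 11.1 makes the primary analysis per-protocol and counts a patient as having received the portal after a login and at least one completed survey.

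**The concern.** Patients know whether they get texts or portal requests, so the only masking available is of the person who collects the outcome. The 24-hour recall is elicited by an interviewer, so an RC who knows the arm can probe, accept or record answers differently without intending to. The same applies, less strongly, to pill counts.

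The per-protocol definition adds to this. The completer lists and Epic look-ups tell the RC role which portal patients have met the receipt rule, so the assessor may know the exposure classification used in the primary analysis as well as the randomised arm.

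At stake is a spurious difference in the outcome on which the trial was sized. It would most plausibly favour SMS or Portal over enhanced usual care (H1, H2). This part of the error is avoidable, whereas the patient's own reporting bias is not.

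**Working it through.** **1. Duties side by side.**

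| RC task | Section | Tells the RC |
|---|---|---|
| Orient patient to texts | 9.14 | SMS arm |
| Create portal account if none exists | 9.15 | Portal arm |
| Receive Erie lists; check Epic | 9.15 | Portal receipt rule met |
| Ask about texts and portal use at each follow-up | 8.1 | Arm and engagement, from 6-8 weeks on |
| Record 24-hour recall | 8.2 | (outcome) |
| Count pills or take the relayed count | 8.2 | (outcome) |

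I found no statement on assessor masking, on splitting these duties, or on the order of items within an interview. The interview scripts are not in the supplied text.

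**2. The plan's own power figure.** Inputs from 11.2: 69% in enhanced usual care, a 12-point difference (so 81%), 172 vs 344 analysed, Type 1 error 2.5%, stated power 80%. Sidedness is not stated.

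- Two-sided 2.5%, pooled null variance: power 78.1%. The detectable difference at exactly 80% is 12.25 points, which rounds to 12.
- One-sided 2.5%: power 85.2%, detectable difference 11.2 points.

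The two-sided reading fits, so it is used below. Sample size: 1204 / 0.80 = 1505, as stated.

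**3. What a spurious difference would do.** Assume no true effect, one yes/no outcome per patient, 69% in both arms, and a reporting shift d in the intervention arm only. The values of d are assumptions; the documents give none.

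SE(d) = sqrt[0.69 × 0.31 / 172 + (0.69 + d)(0.31 − d) / 344], with critical value z = 2.241.

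Rejection probability = Φ(d/SE − 2.241) + Φ(−d/SE − 2.241).

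| d (points) | SE | d/SE | Rejection, unpooled | Rejection, pooled null variance | Share of non-adherent patients misrecorded (d / 0.31) |
|---|---|---|---|---|---|
| 0 | 0.0432 | 0 | 2.5% | 2.5% | 0% |
| 2 | 0.0429 | 0.466 | 4.1% | 4.3% | 6% |
| 3 | 0.0428 | 0.701 | 6.3% | 6.6% | 10% |
| 5 | 0.0425 | 1.178 | 14.4% | 15.2% | 16% |

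The last column shows how much misrecording each row requires. Producing the whole 12-point design difference would take 0.12 / 0.31, about 39%.

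**4. Limits of step 3.** The planned test is a per-protocol mixed model with medications nested in participants (11.1). The table compares two randomised arms with one binary outcome each. It shows how sensitive such a comparison is and does not give the planned test's error rate.

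**The case against.** **Same person, or only same role?** A reader might infer that the RC who set up a patient also interviews that patient at six months. The documents do not say so. With two RCs listed and no separation stated, overlap is likely, but it is an inference. Set-up also does not apply to everyone: enhanced usual care needs none, and a portal account is created only for patients without one.

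**Priming.** It is tempting to say that asking about reminders before recall prompts intervention patients to report good adherence. That needs a question order, and the scripts that would give it were not supplied. The outcome items may already come first. Even so, the fidelity questions at 6-8 weeks would inform the RC before the six-month interview.

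**All four hypotheses.** A reader might extend the direction of bias to H3 and H4. Those compare the combined arm with a single active arm, so the assessor knows that both groups are treated. The direction is uncertain there.

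**No remedy in the analysis.** A reader might conclude that the analysis offers no protection. That goes too far. PDC comes from pharmacy claims without RC elicitation (8.2, 9.17), and the exploratory analyses in 11.1 already plan to compare recall, pill count and PDC. This can expose assessor bias in the recall, though it does not correct it.

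**Structure limits discretion.** Recall is recorded drug by drug as numbers, phone counts follow a standard script, and interviewers are trained and monitored by simulation (8.2, 9.2, 11.4). This narrows the room for drift and stands as a mitigating point, but none of it is masking.

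**Conclusion.** The concern holds at the level of the role. One RC role has arm and engagement information and also collects the outcome used for sizing, and the supplied text states neither masking nor separation. Knowledge of arm at assessment is likely, and for portal patients it may include whether they met the receipt rule.

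The bias would most plausibly favour the intervention in H1 and H2. Its size is not known from the documents. Under the simple comparison above, 2 to 5 spurious points would take the false-positive rate from 2.5% to about 4% to 14%. At the low end the effect is small, and the upper end needs about one in six non-adherent intervention patients to be misrecorded. This is an avoidable weakness that should be closed or disclosed. It is not evidence that any result is biased.

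**What to change.** (a) In the remaining 6-8 week and 6-month interviews, complete and lock recall, ASK-12 and, where done, the pill count in REDCap before the text and portal items open. Check the scripts first; if they already use this order, state it in the protocol. Order alone is not enough, because the RC may know the arm from set-up or from the earlier follow-up.

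(b) Send the Erie completer lists and assign the Epic checks to the data analyst or another team member who does not interview. The project manager is not suitable, since 9.2 includes that role in interviewing.

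(c) Where staffing and language allow, have the follow-up interview done by the RC who did not set up that patient.

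(d) Have the stored pill screenshots, already filed by study ID only, counted by a team member without access to arm.

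(e) Report the claims-based PDC result beside the recall result as a check on assessor bias, for patients whose pharmacy data were released.

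**Cost.** A REDCap form change, a rota rule and re-addressed lists, with no added staff or visits. Scheduling becomes slightly harder, mainly for Spanish-language interviews. Some patients will reveal their arm anyway, (d) reaches video-call counts only, and patients' own reporting bias remains. For interviews already completed, (a) to (c) come too late; (d), where screenshots exist, and (e) can still be done.

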## 8.2 Primary Endpoints.

**Effectiveness Outcomes.** For the outcomes described below, we only include Rx chronic medications. Though we document them, we exclude PRN, as adherence concerns are different.

**Treatment knowledge.** Patients will be asked to identify drug indication; binary classifications will be applied per drug.

**Medication adherence.** The ASK-12 Adherence Barrier Survey assesses patients' general adherence behaviors and barriers to treatment adherence. Adherence will also be measured for each Rx medication using: 1) Self-report of how many pills and how often each medicine was taken over the last 24 hours. The RC will record how many pills were taken at each time for each medicine. Correct dosing will be measured as yes/no per drug, based on having properly demonstrated dose (# pills), spacing (hours between doses), frequency (times per day), and total pills/day, 2) in-person/phone pill counts of all chronic, pill form medicines, using established guidelines employed by our team [R01HS00167; PI [name]], 3) the proportion of days covered (PDC), a measurement of days covered with medication, based on pharmacy claims. This is calculated by summing the number of days' supply obtained by a patient during a given time period and dividing by the number of days for which the medication was prescribed. For each patient, we will assess adherence within drug class. If a patient fills a prescription for a drug and switches to another drug within the same class, all prescriptions will be summed in the numerator. Adherence will be treated both continuously (PDC) and dichotomously (yes/no - PDC  $\geq 80\%$ ). Patients will be asked to sign a release at their first and/or last interview allowing us to obtain fill information from pharmacies used during the study. We will request information from pharmacies 6 months prior to baseline to a year post baseline. If the interview is completed over the phone, patients may receive a pharmacy release form by mail to sign and return to the research team. For the pill count during phone interviews, RCs will read a standardized script to ask patients to count study pills using a standardized procedure. If able, participants will be asked to join a video call so the

RC can take a screen shot of the patient's remaining pills-per bottle. The RC will save the screen shot/photograph to the study project folder within the secure GIM server only using the patient's studyid to identify the photograph. No PHI will be captured in the photograph. If the participant does not have video capabilities, the RC will proceed to explain how the patient can count their pills and relay the number to the RC. This script is outlined in the interview script. For patients consented before May 19, 2020 that complete a phone 6 month, a brief script will be read informing patients of the change in the consent in regards to the pill count. The RC will ask the participant to provide verbal consent to allow the study team to take a screen shot/photograph of the patient's pills during a video call in order for the RC to count the pills after the interview. The patient will be notified that no PHI will be captured in the photograph.

**Medication reconciliation.** Chart reviews will determine whether any discrepancies are present between patient self-report and the chart medication list. Nature of the discrepancy (omission vs. commission) will be recorded.

**Clinical Outcomes.** Systolic/diastolic blood pressure will be collected on all patients during the baseline and 6 month interview. Low-density lipoprotein cholesterol (LDL) will be obtained from patients' electronic health records. Chart review of hemoglobin A1c (hbA1c) will be reviewed for all diabetic patients. Differences will be measured between the last clinical measurement prior to baseline assessment and the last measured value during the study period (closest to 6 month assessment).

